# 4.4 Image Acquisition

Images will be acquired using either a 1-day rest/stress, a 1-day stress/rest, or a 2-day protocol according to local site preferences. Protocols illustrated in Appendix A.

# 4.4.1 Stress Imaging

Patient will be positioned according to standard clinical practice for myocardial perfusion imaging with the heart centered in the field of view. Image data will be acquired in listmode for 11 min starting just prior to tracer injection. There should be no movement of the patient or camera from the start of the vasodilator injection through to the end of image acquisition. Stress will be induced using a vasodilator, either dipyridamole, adenosine, Adenosine Tri-phosphate or regadenoson according to local site preference.

- Dipyridamole: Dipyridamole (0.14 mg/kg/min over 4 or 5 min depending on local laboratory practice) will be given intravenously. 99mTc-tetrofosmin is injected at 3-5 minutes following the end of the dipyridamole infusion. Stress imaging will start immediately prior to the 99mTc-tetrofosmin injection. Aminophylline will be administered intravenously as needed, no earlier than 3 minutes following injection of tracer.
- Adenosine/Adenosine Tri-phosphate: Protocol will follow ASNC guidelines.
- Regadenoson: Protocol will follow ASNC guidelines.

The usual post-stress images (delayed stress) will be acquired as per standard clinical practice.

## 4.4.2 Resting Images

If a stress-first protocol is being used, then the acquisition of additional resting imaging will be decided based on local-site standard clinical practice.

For rest imaging, the patient will be positioned according to standard clinical practice for myocardial perfusion imaging with the heart centered in the field of view. Image data will be acquired in listmode for 11 min starting just prior to tracer injection. There should be no movement of the patient or camera from the start of the tracer injection through to the end of image acquisition.

Acquisition of a clinical resting relative perfusion image (delayed rest) will be acquired as per standard clinical practice.

## 4.4.3 Patient positioning dose

A 40 MBq positioning tracer dose may be injected to aide in positioning of the patient, prior to injection of the tracer for dynamic imaging. If a positioning dose is used, an additional 5-min static image of the tracer will be acquired prior to injection of the tracer used for dynamic imaging. There should be no movement of the patient or camera between the static image of the positioning dose and the acquisition of the dynamic imaging for flow measurement. To note, injection of positioning dose should take place ~20 minutes prior to injection of tracer for dynamic imaging. However, the patient should be on the imaging table only during the static scan prior to the injection for dynamic imaging, and throughout the dynamic imaging which follows.

## 4.4.4 Pre-dynamic imaging

Prior to the second scan of a 1-day protocol (ie the rest imaging in a stress-first protocol), a pre-dynamic static image is required to correct for residual activity from the first injection. A 5 min listmode static acquisition is obtained prior to injection of the radiotracer for dynamic imaging (and prior to injection of the vasodilator in the case of rest/stress protocols). There should be no movement of the patient or camera between the static image and the acquisition of the dynamic imaging for flow measurement.

## 4.5 Image Processing and Analysis

Following acquisition, the listmode data will be rebinned into 9x10s, 6x15s, 4x120s frames. The projection data for each frame will be independently reconstructed using manufacturer supplied MLEM iterative reconstruction that includes point-spread function modeling and a noise-suppression prior. A total of 60 iterations will be used corresponding to the manufacturer recommendation for resting (low-count) studies. Images will be filtered post-reconstruction using a 3D 5th-order Butterworth filter with a cut-off frequency of 0.37 cycles/cm. Images will be reconstructed without corrections (NC), and with attenuation correction (AC) when a CT attenuation scan is available. When applied, AC will be based on a CT scan acquired separately with the patient on the same configuration as used for the SPECT dynamic acquisitions.

The reconstructed dynamic image series will be processed using the kinetic analysis software tools provided by the manufacturer (GE Healthcare). With this semi-automatic software, a 1-tissue-compartment model will be fit to the myocardium time-activity data to generate a parameterized map of the uptake rate constant K1 (ml/min/g) for the heart. K1 values will be scaled to MBF based on the K1-MBF relationship determined from previous single-site comparisons of clinical SPECT and Rb82 PET studies .

## 5. Sample Size and Analysis

Adverse events will be listed on an individual basis. All safety variables and demographic data will be tabulated with descriptive statistics, if appropriate.

Bland-Altman plots will be used to determine significant bias and the coefficient of repeatability of global and regional MBF and MFR measurements for the core versus local reproducibility studies and for measurements of MBF with full and half data reconstructions. The mean difference in MBF between core and local-site processing will be assessed with a paired t-test. A sample size of 25 studies per center provides 88% power (alpha=0.05) to detect a 10% difference, assuming a standard deviation in repeated MBF measurement of 15% (effect size of 0.67). Each center will recruit 5 practice patients and 25- 35 patients for analysis. There will be 6 centers and each center will recruit 30 - 40 patients for a minimum of 180 patients to a maximum of 240 patients(30 practice patients and 150 - 210 patients for analysis). Global and regional MBF at rest and stress will be separately compared. Differences in MFR will be similarly assessed.

To evaluate impact on patient throughput, the following information will be collected for each site and each MBF study:

Time patient enters the room

Time of radiotracer injection (for dynamic imaging sessions)

Start times of each image series (static and dynamic)

Time patient exits the room

Number of MPI studies done per day.

Each site will also provide number of MPI studies done per day for the 2-month period prior to starting to apply the MBF protocol and similar timing and demographic data for 25 standard (non-MBF) MPI studies.

MBF/MFR analysis will be repeated with attenuation corrected images for those data sets which include a transmission imaging.

Image quality will be assessed at the core lab. The following factors will be considered:

- Tracer bolus quality: start of bolus is imaged, bolus duration is appropriate (total activity in the FOV is within 10% of final frame value 3 minutes after start), single peak
- Positioning: Heart is within the quality FOV no truncation.

<sup>1 G\*Power software, version 3.1.3. Faul F, Erdfelder E, Lang A-G, and Buchner A. G\*Power 3: A flexible statistical power analysis program for the social, behavioral, and biomedical sciences. *Behavior Research Methods*, 39:175–191, 2007

- Sufficient injected activity: total counts in the left ventricle in the final 2-min frame is > 1 M
- Artifacts: no evidence of patient motion (or adequate motion correction), no other visible artifacts in the images
- Number of segments with physiologically unreasonable MFR (MFR <0.8 or > 5)

MBF analysis will be repeated for the half-dose MBF data sets. Studies will be read at the Core Laboratory by two experienced readers to provide intra- and inter-observer repeatability of evaluation.

To assess the need for delayed imaging, data sets will be reprocessed at the core lab. The last 6 min of each dynamic acquisition will be used to generate a late-dynamic static MPI image series (immediate imaging). The immediate and delayed images will be reviewed blindly by two experienced readers to provide data on intra- and interobserver repeatability. The summed rest, summed stress, and summed difference scores will be recorded for a 17-segment heart model, along with a final clinical evaluation and a subjective assessment of image quality (on a scale of 1-5). All evaluations will be done by the core lab to ensure consistency in processing and evaluation.

Subjective image quality scale will be:

1 – non-diagnostic: noise or poor contrast in the myocardium prevent clinical interpretation, or artifact or extra-cardiac uptake prevent interpretation of the myocardium.

2 – poor quality: poor contrast and noise in myocardium make interpretation difficult, artifacts and extra-cardiac interference are moderate and reduce confidence in image interpretation

3 - adequate quality: adequate myocardial contrast, artifacts and extra-cardiac interference are mild and may reduce confidence in image interpretation

4 – good quality: good myocardial contrast, artifact and extra-cardiac activity may be present but do not interfere with interpretation

5 – excellent quality: good myocardial contrast, no artifacts, no interference from extra-cardiac activity

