## 1.2 Hypotheses

- a) Primary hypotheses
- 1. Feasibility: It is practical to obtain reliable SPECT measurements of MBF routinely within the workflow of a standard clinical practice.
- 2. MBF reproducibility: Global MBF measured at remote sites will agree within 10% with the same data processed at an expert core laboratory.
- b) Secondary hypotheses
- 1. Impact on throughput: Routine implementation of a SPECT MBF protocol will have at most minimal impact on patient throughput (defined as <10% reduction in patient volumes).
- Delayed imaging: static reconstruction of the last 6 min of the dynamic acquisition will provide images that are clinically equivalent (less than 10% change in patient diagnosis from normal (summed stress score < 4) to abnormal or vice versa), compared to standard static images obtained following a 45-min delay post-injection.
- 3. Half-dose MBF measurement: The difference between MBF measurements with full-data and half-data dynamic acquisitions will be less than or equal to the inter-observer variation in MBF measurements with full-data.

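### Primary hypothesis 2 claims agreement within 10%, but the planned t-test looks for a difference from zero and no rule compares any result with 10%

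*Combined protocol and SAP*

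**What the plan says.** Section 1.2 (Hypotheses) lists two primary hypotheses. The second is that "Global MBF measured at remote sites will agree within 10% with the same data processed at an expert core laboratory". Section 2 also makes consistency of the data a study objective.

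The analysis is in section 5 (Sample Size and Analysis). It begins with agreement plots: "Bland-Altman plots will be used to determine significant bias and the coefficient of repeatability". It continues: "The mean difference in MBF between core and local-site processing will be assessed with a paired t-test". The sizing statement reads "A sample size of 25 studies per center provides 88% power (alpha=0.05) to detect a 10% difference". The variability behind that figure is given separately, as "assuming a standard deviation in repeated MBF measurement of 15" (percent), and the standardized difference is stated to be an "effect size of 0.67". On numbers, "Each center will recruit 5 practice patients and 25- 35 patients for analysis", at 6 centers. On conditions, "Global and regional MBF at rest and stress will be separately compared".

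In the core-versus-local analysis, 10% appears only in the power statement. Its other uses in the document concern throughput, change of diagnosis and bolus quality.

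**The concern.** The hypothesis is a claim of agreement with a numerical limit, whereas the test and its power statement concern detecting a difference. A non-significant paired t-test does not rule out a 10% bias, and a significant one does not show that the bias exceeds 10%. The plan does not say which t-test result would support the hypothesis. The Bland-Altman analysis will supply the estimates needed, but it has no acceptance limit.

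One of the two primary hypotheses therefore has no success criterion. The step from the estimates to a statement of agreement within 10% would have to be chosen after the data are seen. Patient care is not affected, because section 3 describes an observational study with management according to local practice.

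**Working it through.** **Inputs (section 5).** n = 25 per center (up to 35); difference 10%; SD 15%; alpha 0.05; stated power 88%. The null value and the sidedness are not stated.

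**1. The plan's own figure.** Effect size = 10/15 = 0.67, as stated, so 15% is used as the SD of the paired difference. Noncentrality = 0.667 × √25 = 3.33 on 24 df.

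| Reading | Power |
|---|---|
| Two-sided paired t-test against zero | 89.2% |
| One-sided paired t-test | 94.4% |
| Two-sided, SD of difference 15 × √2 = 21.2% | 61.9% |
| Two independent groups of 25 | 63.7% |

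Of these readings, only the first comes close to 88%. That supports taking the null as zero difference.

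**2. What the t-test can say about 10%, per center, SD of the difference 15%.**
- True bias 10%: non-significant with probability 1 − 0.892 = 10.8% at n=25, 5.8% at n=30 and 3.1% at n=35.
- True bias 5%, inside the limit: significant 36% of the time at n=25.

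**3. Where the t-test and a confidence-interval rule part company.** Take a sample SD of 15% and SE = 15/√n. The t-test is significant when the observed mean exceeds t(0.975) × SE. The 90% CI crosses 10% when the mean exceeds 10 − t(0.95) × SE.

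| n | Significant above | 90% CI crosses 10% above |
|---|---|---|
| 25 | 6.19% | 4.87% |
| 30 | 5.60% | 5.35% |
| 35 | 5.15% | 5.71% |

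At n=25 a mean of 4.9% to 6.2% is non-significant although its interval reaches beyond 10%. At n=35 a mean of 5.15% to 5.71% is significant although its interval lies inside 10%.

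Suppose a non-significant test were read as agreement, which the plan does not say. It would then contradict the 90% CI rule at these rates, for true biases of 0, 3 and 5%:
- n=25: 8%, 15% and 21%.
- n=35: 4%, 11% and 16%.

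**4. Pooled analysis.** With n = 6 × 25 = 150, and ignoring variation between centers, an observed mean above about 2.4% is significant. A true 5% bias rejects zero 98% of the time, while an equivalence test against ±10% declares agreement 99% of the time. A significant t-test read as disagreement would then contradict the equivalence result almost every time.

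**5. Power of an equivalence rule.** Power is the probability that the mean ± t(0.95) × s/√n lies wholly within ±10, integrated over the sample SD s. The true biases are assumptions.

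| n per center | Bias 0% | Bias 3% | Bias 5% |
|---|---|---|---|
| 25 | 88.9% | 72.8% | 48.9% |
| 30 | 94.5% | 80.1% | 55.5% |
| 35 | 97.4% | 85.5% | 61.3% |

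If 15% were instead the SD of a single measurement (difference SD 21.2%), power at n=25 and zero bias would be about 48%.

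**6. Individual studies.** At zero bias and SD 15%, the limits of agreement are ±1.96 × 15 = ±29.4%, and P(|difference| < 10%) = 0.495.

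**The case against.** The strongest reply is that the limit is already fixed. Section 1.2 names the quantity, the comparison and the 10%, and section 5 puts Bland-Altman first. On that view the agreement analysis exists and only an acceptance sentence is missing. It is true that the limit is prespecified and that the right estimates will be produced. But which statistic is held against 10% remains open, and the one formal test that is named and powered does not address it.

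A second point is that agreement within 10% could refer to individual studies rather than mean bias, particularly as a coefficient of repeatability is planned. The ambiguity is real. However, section 5 attaches 10% to the mean difference, and at the plan's own SD only about half of the studies would fall within 10% even with no bias. The mean is the workable reading, and the plan should say so.

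Third, the null of zero is inferred rather than stated, and the per-center error rates would change under pooling. Both are correct. The power check supports the inference, and pooling makes the conflict between the two approaches sharper.

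Finally, this is a feasibility study and the correction is one of wording. That limits the cost of the change, but it does not give a primary hypothesis a success criterion.

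**Conclusion.** The concern holds. Primary hypothesis 2 cannot be confirmed by the test planned for it, and no rule links any planned estimate to the 10% limit. This should be corrected before results are seen.

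The error rates depend on 15% being the SD of the paired difference, as the stated effect size implies, on a two-sided test against zero, and on analysis per center. The central point needs none of these: a test of zero difference, whatever its result, does not answer whether agreement lies within 10%.

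**What to change.** Make the primary reproducibility analysis an equivalence analysis of the percent (or log-ratio) local-core difference in global MBF. Declare agreement if the 90% CI for the mean difference lies wholly within ±10%. State in advance:

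1. That the limit applies to mean bias. Report the Bland-Altman limits and the share of studies within 10% descriptively, noting that about ±29% and 50% are expected at SD 15% and zero bias.
2. The level of analysis: either per center, as now sized, with a rule for combining centers, or pooled with allowance for center and per-center results shown.
3. How the rest and stress results combine.
4. That 15% is the SD of the difference, with power restated as equivalence power over a range of true biases.

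The cost is protocol and SAP wording and a less favorable stated power away from zero bias; no new patients or data are needed. Choosing a 95% CI instead would give 78% power at n=25 and zero bias, and n=30 would be needed for 88%.

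The combining rule matters. As an illustration, requiring all six centers to pass on one condition at zero bias, with centers independent, succeeds with the per-center power raised to the sixth power: about 49% at n=25, 71% at n=30 and 85% at n=35.

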For the first time, [name] and our group recently demonstrated the accurate guantification of MBF in a pig model of rest and transient occlusion at stress  using the NM530c camera. The three standard SPECT tracers, TI, 99mTc-tetrofosmin and 99mTcsestamibi, were separately shown to correlate with simultaneously injected microspheres (between r=0.75 and r=0.83; p<0.01 for all). These experiments demonstrated that noninvasive measurement of absolute MBF with a stationary dedicated cardiac SPECT is feasible using common perfusion tracers. In human studies, Ben-Haim et al  showed using 99mTc-sestamibi that an index of global MFR was lower (p=0.02) in regions supplied by obstructed vessels (>50% occluded by coronary angiograph (CA)) than in nonobstructed vessels. Ben Bouallèque et al  showed that the accuracy of regional MFR measured with 99mTc-tetrofosmin was 81% for the detection of obstructed vessels with CA and 85% for the detection of abnormal fractional flow reserve (FFR). Shiraishi et al  found that the accuracy of TI for the prediction of left main or triple-vessel disease, identified by CA, was 80%. Finally, more recent studies have shown that the flow parameter K1 calculated from kinetic analysis of 99mTc-tetrofosmin studies yields an MFRindex that predicts the presence of abnormal MFR as measured by PET Rb and ammonia studies with an accuracy  $\geq$  75% . However, while extremely promising, these studies have all been performed in single centers with relatively small numbers of patients. To successfully translate this technology into a wide-spread, routinely employed

tool for cardiac imaging requires demonstration of the feasibility of implementing an MBF protocol in multiple centers which may or may not have previous experience with MBF imaging.

The primary objective of this study is to perform a multi-center trial to demonstrate the feasibility of measuring MBF and MFR using 99mTc-tetrofosmin and a CZT-based NM530c cardiac SPECT camera.

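### The core-versus-local MBF test is sized for one centre and one measurement; the plan does not say whether it runs per centre or pooled, and gives no method for comparing sites.

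*Combined protocol and SAP*

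**What the plan says.** Section 1.2 states the second primary hypothesis for the remote sites as a group: "Global MBF measured at remote sites will agree within 10% with the same data processed at an expert core laboratory".

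Section 5 names the test: "The mean difference in MBF between core and local-site processing will be assessed with a paired t-test". Its sizing statement is per centre: "A sample size of 25 studies per center provides 88% power (alpha=0.05) to detect a 10% difference". The calculation behind that figure takes 15% as the SD between repeat measurements, which gives an effect size of 0.67. On recruitment it says "Each center will recruit 5 practice patients and 25- 35 patients for analysis", and with six centres this gives 150 to 210 studies for analysis. On the number of comparisons: "Global and regional MBF at rest and stress will be separately compared". MFR is to be handled in the same way. Bland-Altman plots and a coefficient of repeatability are also planned.

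Section 1.1 gives the motive as showing that the protocol can work in "multiple centers which may or may not have previous experience with MBF imaging". Section 3 recruits six sites with differing experience and says that central processing will make a comparison between sites possible. Neither section 3 nor section 5 gives a method for that comparison.

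**The concern.** The hypothesis is at trial level and the sample size is at centre level. Nothing connects the two: no stated level of analysis, no site term, no rule for several tests, and no rule for turning six site results into one conclusion.

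The same data could therefore support different conclusions depending on a choice made after they are seen. Six separate tests may produce a significant difference at some site by chance, or a real difference that is well inside 10%. One pooled test may give a mean near zero while individual sites lie outside 10%. In a study meant to show that centres with differing experience can all produce usable MBF values, the second outcome would be a wrong claim of agreement.

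**Working it through.** **Inputs.** From section 5: n = 25 per centre, 6 centres, SD 15%, difference 10%, alpha 0.05 (sidedness not stated; two-sided assumed). From section 1.2: margin 10%, global MBF only. The documents give no between-site SD; values of 0, 3 and 5 percentage points are assumed below.

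**1. The plan's own figure.** The effect size is 10/15 = 0.67. Exact noncentral-t power for a paired t-test with n = 25 is 89.2% (89.5% using the rounded 0.67). The stated 88% is reproduced to within 2 points. It is sound for one centre and one measurement.

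**2. Per-centre reading, no bias anywhere.** The chance of at least one p<0.05 in k independent tests is 1 - 0.95^k.
- k = 6 (one global measure): 1 - 0.735 = 26%.
- k = 12 (global rest and global stress): 1 - 0.540 = 46%. Rest and stress come from the same patients, so independence is an assumption.

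**3. What p<0.05 means at one centre.** SE = 15/√25 = 3.0 points. The critical value is t(24 df) = 2.064, so an observed mean bias of 2.064 × 3.0 = 6.2% is already significant, although it is inside the 10% tolerance. Conversely, with no bias, the chance that a site mean falls outside ±10% is 2 × (1 - Φ(10/3)) = 0.00086. Over six means that is 1 - (1 - 0.00086)^6, about 0.5%; over twelve, about 1.0%.

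**4. Pooled reading, cancellation.** Take three sites at +12% and three at -12%, with 25 studies each. The pooled mean is 0. The pooled SD is √(225 + 144) = 19.2, the SE is 19.2/√150 = 1.57, and the 95% half-width is 1.976 × 1.57 = 3.1 points. The sampling SE of the mean for these six fixed sites is 15/√150 = 1.22, so the test rejects with probability of about 2 × (1 - Φ(1.976 × 1.57/1.22)), or about 1%. All six sites are out of tolerance and the pooled test says nothing.

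Symmetry is not needed. One site at +15% and five at zero give a pooled mean of 15/6 = 2.5% with a half-width of about 2.6 points, well inside 10%.

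**5. Pooled reading, precision when generalising beyond the six sites.** With between-site SD s, the correct SE is √(s²/6 + 225/150) and the naive SE is about √((225 + s²)/150). The correct half-width uses t(5 df) = 2.571 and the naive one uses 1.976.

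| Assumed s (points) | Naive SE | Correct SE | Ratio | Naive half-width | Correct half-width |
|---|---|---|---|---|---|
| 0 | 1.22 | 1.22 | 1.00 | 2.4 | 3.1 |
| 3 | 1.25 | 1.73 | 0.72 | 2.5 | 4.5 |
| 5 | 1.29 | 2.38 | 0.54 | 2.6 | 6.1 |

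Part of the gap in half-width comes from the change to 5 df, as the first row shows.

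**The case against.** The two failures cannot both occur. The only sizing statement is per centre, which favours a per-centre analysis. That analysis would show each site's bias, so nothing would cancel. This stands: the pooled problem is conditional, and the certain defect is the unstated level of analysis.

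A reader might infer that the primary conclusion has a 26% to 60% chance of being wrong. The documents do not support that. The 60% comes from 18 independent tests including MFR, but hypothesis 2 names global MBF only, and MFR is derived from rest and stress (allowing for that, 18 tests give about 53% to 55%). More basically, p<0.05 against zero is not the 10% criterion; step 3 shows how rarely an unbiased site mean would fall outside it.

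A reader might also infer that pooled error bars are about half their proper width. That needs an assumed site SD near 5 points and six sites treated as a random sample of sites. For a statement limited to these six sites, the pooled SE is not too small.

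The ±12% pattern is deliberately severe. It would widen the Bland-Altman limits from about ±29% (1.96 × 15) to about ±38% (1.96 × 19.2), which an attentive analyst might notice. However, the plan sets no acceptance limit for those plots and does not split them by site.

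Finally, features of the plan restrain site bias: semi-automatic software from one manufacturer (section 4.5), and five start-up studies per site with core-lab support, excluded from the analysis (section 3). Nor do the documents say that each site uses a single operator. These points make large site biases less likely. They do not supply the missing analysis.

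**Conclusion.** The concern holds in a limited form and should be fixed. Section 5 applies a test sized for one centre and one measurement to a claim about all remote sites, without a level of analysis, a site-level criterion or a method for the between-site comparison that section 3 anticipates. This goes beyond loose wording, because a pooled analysis consistent with the text could miss sites that are all outside 10%.

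The sizes differ in standing. The 26% (6 tests) and 46% (12 tests) assume independence and concern false signals against zero. The cancellation result uses only the plan's SD and 6 × 25 design, with illustrative biases. The SE ratios of 1.00, 0.72 and 0.54 depend on an assumed site SD and on generalising beyond the six sites. The stated 88% power is not in error; it simply does not describe hypothesis 2 as a whole. In an observational feasibility study whose data allow the repair, this does not threaten the trial's validity.

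**What to change.** Amend section 5 as follows.

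- For global rest MBF and global stress MBF, report each site's mean local-minus-core percentage difference with a 95% CI set against ±10%, labelled by the site's prior MBF experience.
- Report the overall difference from a model with a site effect. If the result is to be generalised beyond the six sites, make that effect random, give the between-site SD, and use a small-sample CI (about 5 df).
- Judge agreement by confidence intervals against ±10%, not by p<0.05 against zero.
- Do not let one site's point estimate veto agreement. At an assumed site SD of 5, a site mean has SD √(25 + 9) = 5.83 and falls outside ±10% with probability 0.086, so a veto would block agreement 1 - 0.914^6 = 42% of the time per measure.
- Treat MFR and regional comparisons as descriptive.
- Restate the 88% power as applying to one centre and one measurement.

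This would expose the ±12% pattern. Each site's interval would be about 12 ± 6.2 in absolute size, not contained in the margin. The random-site interval would also fail: the SD of the site means is √(6 × 144/5) = 13.1, the SE is 13.1/√6 = 5.4, and the half-width is 2.571 × 5.4, about 14 points.

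The cost is SAP wording and standard software, with no new data. The downside is a wider overall interval (half-width about 6 points at an assumed site SD of 5, still narrower than the 10% margin) and an imprecise between-site SD with only six sites.
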